### Authorities

The Research Monitor's primary responsibilities relate to the proper conduct of the investigation and the welfare of the subjects who are involved. As such, [name] will have the authority to suspend research associated with the project when any of the following occurs:

1. Enrollment criteria are inconsistent with those specified in the research protocol in 2 or more enrolled subjects in 2 consecutive quarters of the funding period
2. Written informed consent is not obtained for any subject in any quarter of the funding period
3. Failure by the research team to report any adverse event appropriately as per UNC-CH Biomedical IRB guidelines
4. Multiple adverse events are reported (3+) in a given quarter of the funding period
5. Multiple adverse events are reported within a given intervention group (5+) across the entire funding period

Any subjects who experience adverse events will be referred to UNC Student Health Services, the Stallings-Evans Sports Medicine clinic (located in the building adjacent to Fetzer Hall where the Neuromuscular Research Laboratory is located), or Emergency Medical Services depending on the nature and severity of the adverse event. All individuals involved with data collection are certified in CPR and First Aid.

## **10 DATA COLLECTION AND MANAGEMENT**

All data will be deidentified. Subjects will be identified only by a subject ID# to which their personal information will not be linked. Deidentified data files (e.g. gait biomechanics data trials) will be stored and backed up in numerous password-protected locations including computers in the Neuromuscular Research Laboratory, external hard drives, and the UNC-CH Research Computing Mass Storage System.

## **11 RECRUITMENT STRATEGY**

The ACLR cohort for this investigation will consist of volunteers from the faculty, staff, and student populations at UNC-CH and the surrounding area. Potential subjects will be recruited verbally from classes following approval by course instructors. At this time, potential subjects will be read a standard recruitment script and will be allowed to ask any questions pertaining to the investigation. Individuals who are interested in participating will be provided the PI's contact information and asked to contact the PI to address any additional questions regarding the study and to schedule data collection. Additionally, subjects will be recruited via informational flyers posted on the UNC-CH campus and in local rehabilitation clinics, including the Durham VA Medical Center, and via an informational email posted on the UNC-CH server. Subjects will also be recruited from UNC Orthopedics ([name]) and Triangle Orthopaedic Associates ([name]). All subjects must receive physician approval to return to regular, unrestricted physical activity to be eligible for participation. Drs. [name] and [name] will provide subjects with information regarding participation in the study following the subject's clinical visit at which this approval is obtained. [name] (joint appointment at Durham VA Medical Center) will serve in this same capacity for recruiting subjects from the Durham VA Medical Center. We will also submit a request to the Carolina Data Warehouse for Health to generate a list of patients with ACL reconstruction within the past 5 years. This patient list will include names and multiple forms of contact information that will be used to contact potential subjects via telephone, letter/US Mail, or email depending on the available contact information to determine the individual's interest in participating in the study. [name] will perform similar retrospective chart reviews at Triangle Orthopaedic Associates to identify potential subjects. The Healthy Control cohort for this investigation will consist of volunteers from the faculty, staff, and student populations at UNC-CH and the surrounding area. Potential subjects will be recruited verbally from classes following approval by course instructors. At this time, potential subjects will be read a standard recruitment script and will be allowed to ask any questions pertaining to the investigation. Individuals who are interested in participating will be provided the PI's contact information and asked to contact the PI to address any additional questions regarding the study and to schedule data collection.

Drs. [name] and [name] each perform approximately 50 ACLR procedures annually, and each of their orthopaedic practices (UNC Orthopaedics and Triangle Orthopaedic Associates, respectively) performs more than 200 ACLR procedures annually. The Durham VA Medical Center performs approximately 10 ACLR procedures each year in veterans who meet the inclusion criteria. These data indicate that as many as 1,230 potential subjects will be available for recruitment via our clinical collaborations during the funding period (410/year x 3 years). Additionally, we will perform retrospective chart reviews in each of these clinical settings to identify potential subjects. Lastly, we will also recruit potential subjects from local rehabilitation clinics and from the University community. As part of ongoing research in our laboratories we have recruited 40+ individuals in the past year who meet these criteria from the University community alone without taking advantage of the aforementioned clinical collaborations that have been established for the project or targeting local rehabilitation clinics. As such, we are highly confident that we can recruit the necessary sample for the investigation.

## **12 CONSENT PROCESS**

Upon reporting to the laboratory, and prior to screening and data collection procedures, all subjects will be required to read and sign the approved informed consent document. Members of the research team will oversee this process to ensure any questions subjects have are answered prior to providing written informed consent. Drs. [name] (PI), [name] (Co-Investigator), and [name] (co-investigator), and all research assistants will be obtaining consent. As the PI teaches courses in which potential subjects may be currently enrolled or enrolled in the future, these individuals will be informed that their participation or the lack thereof will not influence their academic standing. Similarly, UNC-CH employees will be informed that their participation or the lack thereof will not influence their employment status. Lastly, subjects recruited from orthopaedic and rehabilitation clinics will be informed their clinical care will not be influenced by their participation or the lack thereof.

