### **3.2 Allocation to Treatment Groups and Blinding (if applicable)**

Stratified randomization into 3 groups of equal size (n = 25) will be performed using a computer generated randomization algorithm. This algorithm will ensure stratification with respect to age and time since ACLR.

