## **4.2 Intervention/Treatment procedures**

### **Vibratory Interventions**

All interventions will be performed with subject standing on a WBV device in approximately 40° of knee flexion, but the WBV device will only be "on" for the WBV group. Subjects assigned to the WBV group will receive a vibratory stimulus (30Hz, 2g) applied for 1 minute. This exposure will be repeated 6 times with 2 minutes of rest between exposures. Subjects in the LMV group will receive an identical stimulus (30Hz, 2g) via a custom-built vibrator secured over the distal anterior thigh. We have previously

demonstrated that these interventions enhance quadriceps activity. Subjects in the Control group will perform these exact same procedures with the exception that no vibratory stimulus will be applied. All interventions will be conducted by a graduate research assistant, and the PI will be blinded to group assignment.

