## **8 STUDY INTERVENTION ADMINISTRATION(if applicable)**

This preclinical investigation will utilize a single-blind randomized controlled experimental design whereby 75 individuals with primary unilateral ACLR will be randomly assigned to WBV, LMV, and Control groups. Stratified randomization into 3 groups of equal size (n = 25) will be performed using a computer generated randomization algorithm to ensure stratification with respect to age and time since ACLR. All individuals involved with data collection and analysis will be blinded to group allocation.

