## **9 SAFETY MANAGEMENT**

### **Research Monitor Responsibilities and Authorities**

[name] from the UNC-Chapel Hill Department of Orthopaedics will serve as the Research Monitor for this investigation. [name] possesses both the research ethics and medical expertise necessary to carry out this role. The PI will provide the Research Monitor a summary report during each quarter of the funding period that details information necessary for him to perform the following responsibilities:

1. Enrollment data
  - a. # of subjects (total and per group)
    - i. The Research Monitor will be unblinded to group, but the PI and all research team members involved with data collection will remain blinded.
    - ii. Groups will be identified by number only (e.g. Group 1 = Control, etc.) in reports generated by the PI, and the Research Monitor will be provided a key to decode group membership by the unblinded research assistants who are delivering the interventions.
    - iii. The Research Monitor will evaluate enrollment data to ensure the enrollment rate is consistent with the project timeline (i.e. 30 subjects per year for Years 1 and 2; 15 for Year 3).
  - b. The Research Monitor will verify subjects meet the enrollment criteria
    - i. Relevant data regarding the inclusion/exclusion criteria (e.g. age, KOOS scores, CAR, time since ACL reconstruction surgery, etc.) will be entered in an electronic data management system (Epi Info, Centers of Disease Control and Prevention). This system is capable of generating spreadsheets for data organization. These spreadsheets will be provided to the Research Monitor to permit verification of the enrollment criteria.
2. Verify consent
  - a. Data entry in Epi Info will require the member of the research team who is entering a given subject's data to verify (yes/no) that written informed consent was obtained. This individual will also be required to enter his/her initials in Epi Info to confirm that consent was obtained. The Research Monitor will verify that each subject has been consented based on these data contained in the quarterly report.

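### Unblinded research assistants who deliver the interventions may also obtain consent, and assignment is not placed after eligibility, which leaves an opening for selection at entry

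*Combined protocol and SAP*

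**What the plan says.** **Who obtains consent.** Section 12 lists the principal investigator, two co-investigators and the assistants: "all research assistants will be obtaining consent". Consent comes first: "Upon reporting to the laboratory, and prior to screening and data collection procedures, all subjects will be required to read and sign" the consent form.

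**Who knows the groups.** Section 9 says the Research Monitor "will be provided a key to decode group membership by the unblinded research assistants who are delivering the interventions". Section 4.2 agrees on who delivers: "All interventions will be conducted by a graduate research assistant, and the PI will be blinded to group assignment".

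**How subjects are allocated.** Section 3.2: "Stratified randomization into 3 groups of equal size (n = 25) will be performed using a computer generated randomization algorithm", and "This algorithm will ensure stratification with respect to age and time since ACLR". It gives no stratum cut-points, block size, holder of the sequence or time of assignment. Section 4 has subjects receive their assigned intervention in Session 2, so assignment happens at some unstated point before that.

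**Whom the blinding covers.** Section 8: "All individuals involved with data collection and analysis will be blinded to group allocation". Section 9 extends blinding to the principal investigator and to team members who collect data. Neither section mentions the people who obtain consent.

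**The concern.** Read together, sections 9 and 12 allow a person who knows which groups earlier subjects received to obtain consent from the next one. With equal group sizes fixed in advance, and more so with small blocks within strata, earlier assignments partly predict later ones. A consent-taker with a view about the likely next group could, even without intending to, encourage one person and discourage another.

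Two features of the trial make this relevant. The team has a stated expectation about who benefits: section 6.2 (Aim 3) hypothesises larger gains in people with worse quadriceps function, worse proprioception and lower KOOS scores. And section 6.3 names quadriceps function as the primary outcome, which section 4.1 measures during maximal voluntary contractions, so effort could plausibly matter. Section 6.2 adjusts for the pre-test value and for other pre-test variables found to be imbalanced. That handles measured differences. It cannot remove unmeasured ones such as motivation. Blinding of outcome assessment, and stratification itself, do not address selection at entry.

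**Working it through.** **Step 1: do the two roles overlap?** Section 12 names all research assistants. Section 9 identifies some research assistants as unblinded and delivering the interventions. The second set lies inside the first, and no section takes it out. The blinding statements in sections 4.2, 8 and 9 reach the principal investigator, data collection and analysis, but not consent.

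**Step 2: is allocation restricted?** Three groups of 25 give 3 × 25 = 75, which matches the planned total. The groups are to be equal and the randomisation stratified, so successive assignments are not independent.

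**Step 3: how much do past assignments reveal?** The documents give no block size, so this step rests on assumptions: the guesser knows all past assignments and the block structure, and blocks are filled.

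Let the assignments still to be made in a block be (a, b, c), with t = a + b + c. The best guess is the group with most remaining, and it is right with probability max(a, b, c)/t. Averaging over all orders and positions gives the expected share correct.

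- Blocks of 3: the first guess is right with probability 1/3, the second 1/2, the third 1. The average is (1/3 + 1/2 + 1)/3 = 1.833/3 = 61.1%.
- Blocks of 6: the six positions give 1/3, 2/5, 1/2, 8/15, 3/5 and 1. The sum is 3.367, and 3.367/6 = 56.1%.
- Larger blocks, by exact enumeration with the same rule:

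| Assumed restriction | Best guess correct | Next assignment certain | At least one group ruled out |
|---|---|---|---|
| Blocks of 3 | 61.1% | 33.3% | 66.7% |
| Blocks of 6 | 56.1% | 20.0% | 46.7% |
| Blocks of 9 | 53.2% | 14.3% | 35.7% |
| Blocks of 12 | 51.2% | 11.1% | 28.9% |
| Only 25/25/25 overall (one block of 75) | 41.6% | 2.0% | 5.7% |
| Chance | 33.3% | – | – |

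**Step 4: in subjects.** Over 75 assignments, chance gives 75 × 1/3 = 25 correct guesses. The range gives 75 × 0.416 = 31 to 75 × 0.611 = 46, that is, about 6 to 21 more than chance. An assistant who knows only some past assignments, or does not know the blocks, would do less well.

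**Step 5: from predictability to bias.** The documents give nothing from which to estimate how often a consent-taker would act on a guess, or by how much the groups would then differ. No figure for bias in the treatment contrast can be derived. No power or sample-size figure is affected.

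**The case against.** The strongest reply is that the opening is narrow.

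- **Recruitment and scheduling.** Section 11 uses a standard script for classroom volunteers and sends them to the principal investigator, who is blinded, to schedule. Clinic patients receive their information from clinicians. No section gives recruitment or scheduling to the intervention assistants; for patients found through record searches, the documents leave partly open who makes contact. This stands. The documented contact at entry is consent, from someone who has already come to the laboratory.
- **Eligibility.** After consent, entry depends on age, time since surgery, KOOS cut-offs and a measured CAR, and the Research Monitor checks the criteria. This also stands. It narrows discretion after consent but does not stop encouragement or discouragement during it.
- **Blinded data collectors may in practice take consent.** Session 1 combines consent with assessments that blinded staff should perform, so the same staff might do both. Section 12 does not say so, and its wording includes every assistant.
- **What the assistants know.** A reader might infer that they know every earlier assignment by age and time-since-surgery stratum. The documents do not say this. Section 9 describes a key that decodes group numbers and refers to assistants in the plural. Section 4.2 could mean that one assistant treats everyone, but knowledge of strata or of the sequence would still be an inference.
- **The 61%.** A reader might take this as the size of the problem. It is the top of a range, reached only with the smallest possible block, and no section says that blocks are used.

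An independent holder of the sequence may exist in practice. The plan describes none, and such a person would hide the next assignment without preventing guesses from past ones.

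**Conclusion.** The concern holds as a gap in allocation concealment. The consent rule as written admits unblinded staff to subject entry, and the plan does not fix assignment after eligibility. This is more than missing detail, because section 12 positively assigns consent to every assistant.

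The predictability is about 42% to 61% correct against 33% by chance, conditional on full knowledge of past allocations and of a block structure that the documents do not state. The range covers the restrictions tried and is not a bound on every possible algorithm.

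The documents do not support a claim that selection has occurred, or any figure for the resulting bias. The opportunity is limited by the eligibility cut-offs and by the route through the blinded principal investigator for some volunteers. The change is still worth making before enrolment, because it is cheap and adjustment for pre-test values cannot repair unmeasured imbalance afterwards.

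**What to change.** - **Section 12:** limit consent to the principal investigator, the co-investigators and any research assistants who neither deliver interventions nor hold the group key.
- **Sections 3.2 and 4:** state that each assignment is released to the intervention assistant only after consent and Session 1 eligibility have been recorded.
- **Section 3.2:** state that any block details are withheld from staff who obtain consent or screen.

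These parts work together. Separating the roles removes knowledge of past assignments from consent, late release hides the next assignment, and withholding block details weakens any remaining guess.

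The cost is protocol wording and a rota change. The downside is less flexibility over who can consent on a given day. The documents do not identify any blinded research assistants, so the plan should not count on them, but the investigators already listed in section 12 can obtain consent. Sample size, outcomes and analysis are unchanged.

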## **13 PLANS FOR PUBLICATION**

We intend to draft 3 primary manuscripts for publication that will detail, respectively, 1) the effects of the interventions on gait biomechanics, 2) the effects of the interventions on somatosensory function, and 3) patient characteristics that influence the efficacy of the interventions.

